3.5.4.1.2 Pediatric Population

All pediatric subjects included in the study will be evaluated for RASs. There will be no efficacy assessment of durability of long-term SVR in this population as enrollment in this study will be limited to pediatric subjects who were virologic failures and had emergent RAS present at FW12 in the prior treatment study.

3.5.4.2 Safety Analysis Populations

3.5.4.2.1 Adult Population

All data from adult subjects who sign an informed consent/assent for this study will be included in the safety evaluation.

3.5.4.2.2 Pediatric Population

All data from pediatric subjects who sign an informed consent/assent for this study will be included in the safety evaluation.

3.5.5 Statistical Methods

No hypothesis testing will be performed in this non-drug long-term follow-up study. Efficacy and safety data will be summarized using descriptive statistics. As subjects are permitted to participate in other treatment studies for HCV concurrently with this protocol, all follow-up data collected after subjects started HCV treatment will be summarized separately.

3.5.5.1 Statistical Methods for Efficacy Analyses

3.5.5.1.1 Adult Population

The efficacy endpoint of time to viral relapse will be summarized using Kaplan-Meier methodology at fixed time points (6-month intervals). These time points represent the follow-up time since the last dose of study therapy taken in the prior treatment study. Subjects who do not relapse during the current study will be censored on the last visit date. Any subject who relapsed between the end of the prior treatment study and entry into this study will be considered a relapse at the time of study entry.

Relative days ranges, calculated from the date of last dose of therapy taken in the prior treatment study, will be used to define the months of follow-up for the analysis of time to viral relapse. These relative day ranges will be continuous and stretch from the date of last dose in the prior treatment study to the midpoint between the first 2 time points (i.e. 6 and 12 months --> midpoint: 9 months), from midpoint to midpoint between each successive pair of time points and above the last midpoint for the last time point. As the screening visit could occur within 1-year of the last dose of therapy taken in the prior treatment study for subjects enrolled prior to AM 03, certain subjects may have a follow-up time close to 6 years. Day ranges are therefore defined up to Month 72 and are provided in [Table 7](#).

Table 7

Definition of Months of Follow-up for Time to Relapse Analysis

Month	Relative Day Range ^a
6	1 to 274
12	275 to 456
18	457 to 638
24	639 to 821
30	822 to 1003
36	1004 to 1186
42	1187 to 1368
48	1369 to 1550
54	1551 to 1733
60	1734 to 1915
66	1916 to 2098
72	≥ 2098

^a Day range relative to date of last dose of therapy taken in the prior treatment study.

Missing Values

Only observed data will be included in the analyses. For the time to relapse analysis, subjects missing an HCV RNA evaluation at any particular visit will be considered a non-relapser for that visit. Subjects who discontinue the study without relapsing will be censored at the time of discontinuation.

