2. CORE PROTOCOL

2.1 OBJECTIVES AND HYPOTHESES

2.1.1 Primary

2.1.1.1 Adult Population

In HCV-infected subjects who received at least 1 dose of GZR in a previous study:

1. **Objective:** To evaluate the durability of response in subjects who achieved SVR₂₄ in the prior treatment study and at the time of entry into PN017 were HCV ribonucleic acid (RNA) <lower limit of quantification (LLoQ) (either target not detected [TND] or target detected, unquantifiable [TD(u)]).
2. **Objective:** To evaluate the presence of treatment-emergent antiviral resistance to NS3/4A, NS5A and/or NS5B regions, (as applicable) and determine if there is a reversion to wild-type pattern within the 3-year time frame of this long-term follow-up study (or 5-year time frame for subjects from PN052) in subjects with virologic failure in the prior treatment study and with HCV RNA ≥ 1000 IU/mL in Protocol 017.
3. **Objective:** To evaluate the long-term safety.

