2.3 SUBJECT EXCLUSION CRITERIA (ADULT AND PEDIATRIC POPULATIONS)

Exclusion criteria apply to both the adult and pediatric populations.

1. **Adult subjects:** In the opinion of the investigator, subject is mentally or legally incapacitated at entry into PN017.

Pediatric subjects: The subject has significant emotional problems or a clinically significant psychiatric disorder that may interfere with participant treatment, assessment, or compliance with the protocol.

2. Subject has received HCV therapy after completion of the prior treatment study and before entry into PN017.
3. Starting with AM 03: subjects who failed therapy due to re-infection, defined as:
 - an HCV RNA sample with a different genotype than the baseline genotype in the prior treatment study, or

- an HCV RNA sample determined to be reinfection by phylogenetic analysis with comparison to the baseline sequence in the prior treatment study.

4. Starting with AM 03: subjects who failed therapy in the prior treatment study and received retreatment with HCV therapy.

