2.5 LIST OF EFFICACY/PHARMACOKINETIC/IMMUNOGENICITY MEASUREMENTS

The following measurements are applicable for the adult and pediatric populations.

HCV Genotype

Samples will be genotyped using the Food and Drug Administration (FDA) approved Abbott HCV Real Time Genotype II assay which detects HCV GT1a, 1b, 2, 3, 4, 5, and 6 through the use of genotype-specific fluorescent-labeled oligonucleotide probes in a real-time reverse transcriptase-polymerase chain reaction (RT-PCR) assay. The RT-PCR reaction uses 3 sets of HCV specific amplification primers targeting the conserved 5' untranslated region (for all genotypes) and NS5B regions from GT1a and 1b. The assay has accuracy of >96% for GT1, 1a, 1b, 2, 3 and 4, 89% for GT5 and 83% for GT6 with 100% specificity in HCV serologically negative plasma samples. Phylogenetic analyses will be performed using sequences for NS3/4A, NS5A and NS5B to ensure accurate assignment of sample genotype/subtype.

HCV RNA

HCV RNA in plasma will be measured using a COBASTTM AmpliPrep/COBASTTM TaqmanTM HCV Test, v2.0 ® assay with a LLoQ of 15 IU/mL. HCV RNA definitions are presented in [Table 1](#).

Table 1

HCV RNA Definitions

Abbreviation	Definition	HCV RNA Level
TND	Target not detected	HCV RNA not detected
TD(u)	Target detected, unquantifiable	HCV RNA < LLoQ
TD(q)	Target detected, quantifiable	HCV RNA ≥ LLoQ

HCV=hepatitis C virus; LLoQ=lower limit of quantification; RNA=ribonucleic acid

For subjects enrolled prior to AM 03, durability of virologic response will be assessed in all subjects who are HCV RNA <LLoQ (either TND or TD[u]) on Day 1 of entry into this protocol and excluding any subject who is TND/TD(u) due to having received an anti-viral treatment after having failed previous therapy in the parent study.

Failure of therapy due to relapse more than 24 weeks after the end of therapy (termed late relapse) in this group of subjects will be measured as an HCV RNA that is confirmed to be ≥LLoQ and is not due to a new infection or re-infection. Confirmation is defined as an HCV RNA that is target detected, quantifiable (TD[q]) from a separate blood draw repeated in approximately 4 weeks.

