6.3 LIST OF ABBREVIATIONS

Abbreviation/Term	Definition
AE	Adverse event
ALT	Alanine aminotransferase
AM	Amendment
aPTT	Activated partial thromboplastin time
AST	Aspartate aminotransferase
CFR	Code of Federal Regulations
CI	Coordinating Investigator
CKD	Chronic kidney disease
CRF	Case report form
CSR	Clinical study report
DAA	Direct-acting antiviral
DNA	Deoxyribonucleic acid
EBR	Elbasvir; MK-8742
ECI	Event of clinical interest; selected adverse experiences
eCRF	Electronic case report forms
eGFR	estimated glomerular filtration rate
EMA	European Medicines Agency
ERC	Ethical review committee
FBR	Future Biomedical Research
FDA	Food and Drug Administration
FDAAA	Food and Drug Administration Amendments Act
FW	Follow-up week
GCP	Good Clinical Practice
GT	Genotype
GZR	Grazoprevir; MK-5172
HCT	Hematocrit
HCV	Hepatitis C virus
Hgb	Hemoglobin
IB	Investigators brochure

Abbreviation/Term	Definition
ICH	International Committee on Harmonisation
IEC	Independent ethics committee
INR	International normalized ratio
IRB	Institutional review board
IXRS	Interactive voice/web response system
LLoQ	Lower limit of quantification
MELD	Model for End-Stage Liver Disease
NS	Nonstructural protein
PD	Pharmacodynamic
PGt	Pharmacogenetics
PK	Pharmacokinetic
PN	Protocol number
PR	Pegylated-interferon + RBV
PT	Prothrombin time
RAP	Resistance associated polymorphisms
RAS	Resistance associated substitution
RBC	Red blood cell
RBV	Ribavirin
RNA	Ribonucleic acid
RT-PCR	Reverse transcriptase-polymerase chain reaction
RZR	Ruzasvir; MK-8408
SAE	Serious adverse event
SAP	Statistical analysis plan
SOP	Standard operating procedures
SVR	Sustained virologic response
SVR ₁₂	Sustained virologic response 12 weeks after the end of all study therapy. The subject has HCV RNA < LLOQ [either TD (u) or TND] 12 weeks after the end of all study therapy
SVR ₂₄	Sustained virologic response 24 weeks after the end of all study therapy. The subject has HCV RNA < LLOQ [either TD (u) or TND] 24 weeks after the end of all study therapy

Abbreviation/Term	Definition
TD(q)	Target detected, quantifiable
TD(u)	Target detected, unquantifiable
TIA	Transient ischemic attack
TND	Target not detected
UPR	Uprifosbuvir; MK-3682
US	United States
WBC	White blood cell

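### The plan conflicts on whether SVR subjects already quantifiable at PN017 entry count in the primary relapse analysis; if they are left out, a Kaplan-Meier curve with everyone at risk from last dose understates late relapse

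*Combined protocol and SAP*

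**What the plan says.** **Clock and censoring.** Section 3.5.5.1.1 measures time to relapse from last dose in the prior study ("These time points represent the follow-up time since the last dose of study therapy taken in the prior treatment study") and ends follow-up as follows: "Subjects who do not relapse during the current study will be censored on the last visit date". No delayed-entry risk set is described there or elsewhere.

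**Entry time.** Before Amendment 03, Visit 1 could fall well after follow-up week 24 (FW24): "As the screening visit could occur within 1-year of the last dose of therapy taken in the prior treatment study". The current window (Section 2.2, criterion 2) is 3 months from the last prior-study visit.

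**Gap relapses** (between the end of the prior study and PN017 entry). Section 3.5.5.1.1 says that a subject with such a relapse "will be considered a relapse at the time of study entry".

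**Who is analysed.** Two definitions stand side by side.
- Objective 1 (Section 2.1.1.1) takes subjects who achieved SVR24 and "at the time of entry into PN017 were HCV ribonucleic acid (RNA) <lower limit of quantification (LLoQ". For subjects enrolled before Amendment 03, Section 2.5 likewise requires a value below LLoQ on Day 1 of PN017.
- Section 2.7.1.1 with its Table 3, and Section 3.5.4.1.1, require SVR in the prior study and no new HCV therapy. They set no HCV RNA condition at entry.

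**Retreatment.** Exclusion criterion 2 (Section 2.3) bars a subject when "Subject has received HCV therapy after completion of the prior treatment study and before entry into PN017". Sections 2.7.1.1 and 3.5.4.1.1 also remove retreated subjects from the analysis population.

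**The concern.** An untreated SVR24 subject who is quantifiable at Visit 1 is an event under Section 3.5.5.1.1 and is outside the analysis under Objective 1. Two programmers could follow the document and produce different primary curves.

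The Objective 1 reading also creates a selection problem. A subject must be relapse-free at Visit 1 to be analysed, so no relapse in that subject can be observed before Visit 1. The plan still counts the subject in every risk set from last dose. Relapse rates between FW24 and the last entry dates are then diluted by people who could not yet have an event, and the deficit carries through the rest of the curve. Retreated gap relapsers are lost under either reading.

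Durability is a primary objective, no hypothesis test is planned (Section 3.5.5), and no separate SAP will be issued (Section 3.5). This curve is therefore the main durability result, and this document is the place to settle it.

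**Working it through.** **1. The plan's own figures.** Table 7's upper limits are the midpoint months 9, 15, ..., 69 multiplied by 30.4 days and rounded: 9 x 30.4 = 273.6, giving 274; 15 x 30.4 = 456; 69 x 30.4 = 2097.6, giving 2098. All 11 limits reproduce. The documents give no relapse rate, sample size or event count, so the rates below are assumptions shown as a range.

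**2. Inputs.** SVR24 is defined in Section 6.3 ("Sustained virologic response 24 weeks after the end of all study therapy"), so late relapse is taken to start at day 24 x 7 = 168. Entry is taken as uniform over days 168-259 (a 3-month window, 168 + 91) or days 168-365 (the pre-Amendment 03 limit). Follow-up after entry is taken as uniform over 180-1095 days.

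**3. Mechanism.** Each event time t multiplies the curve by 1 - d(t)/n(t).
- *Gap relapses counted at entry:* between last dose and day 168 there are no events and no censoring. Every n(t) is the same whether the clock starts at last dose or at FW24, so the origin changes only the time label.
- *Gap relapsers excluded:* at a time t before all have entered, the valid factor uses only those already entered, d/n_entered. The planned factor uses d/(n_entered + n_not yet entered), which is smaller. Once everyone has entered the factors agree, so the early deficit persists.

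**4. Expected deficit.** It is about the mean relapse risk over a gap that is uniform on 0 to w days, with w = 91 or 197 (365 - 168).
- Constant rate r per year: r x (w/2)/365.25. At 1%/year this gives 1% x 45.5/365.25 = 0.12% and 1% x 98.5/365.25 = 0.27%.
- Front-loaded total p, exponential with mean 90 days after FW24: p x [1 - (90/w)(1 - exp(-w/90))]. For p = 1% this gives 0.37% and 0.59%; for p = 2%, 0.74% and 1.19%.

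**5. Simulation.** One million SVR24 subjects per scenario; cumulative relapse at day 1095 with gap relapsers excluded:

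| Assumed relapse | Entry window | Planned KM | Delayed-entry KM | Shortfall (points) |
|---|---|---|---|---|
| 0.2%/year | 3 months | 0.482% | 0.507% | 0.025 |
| 0.2%/year | to 1 year | 0.454% | 0.505% | 0.051 |
| 1%/year | 3 months | 2.393% | 2.504% | 0.111 |
| 1%/year | to 1 year | 2.221% | 2.480% | 0.259 |
| Front-loaded 1% | 3 months | 0.623% | 0.992% | 0.369 |
| Front-loaded 1% | to 1 year | 0.406% | 1.009% | 0.603 |
| Front-loaded 2% | 3 months | 1.255% | 1.970% | 0.715 |
| Front-loaded 2% | to 1 year | 0.806% | 1.960% | 1.154 |

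The shortfalls agree with step 4.

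**6. The other reading.** With every gap relapse counted at entry, the planned estimate against the simulated truth at day 1095 was 2.518% against 2.505% (1%/year, 3-month window) and 1.010% against 1.010% (front-loaded 1%, 1-year window). Restarting the clock at FW24 gave identical values throughout. The only distortion was dating: with entry up to 1 year and front-loaded 1%, the estimate at day 274 (the end of Table 7's Month 6 row) was 0.380% against 0.708%. By day 365 both were 0.900%. With the 3-month window the two already agreed at day 274 (0.699%).

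**The case against.** The best defence is that the analysis section already deals with gap relapses. Section 3.5.5.1.1 counts them at entry, and the populations in Sections 2.7.1.1 and 3.5.4.1.1 would admit untreated gap relapsers. On that text the curve recovers fully by day 365 in the scenarios run. The analysis is also descriptive, with no power target, and Section 1.3.1 describes SVR after DAA treatment as durable for years, so the low-rate rows may be the most realistic.

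Much of this stands. A reader might infer that the last-dose origin itself depresses the curve, that every analysed subject is guaranteed relapse-free to Visit 1, or that the curve stays too low whatever rule is used. The documents do not support these inferences. An event-free lead-in leaves the estimate unchanged, and under the Section 3.5.5.1.1 rule there is no lasting deficit when all gap relapses are captured.

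The defence does not remove the conflict. Objective 1 and Section 2.5 exclude the subjects that the rule would count. The rule also cannot recover relapsers who were retreated before entry, or who never enrolled.

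**Conclusion.** The point holds as an inconsistency with a conditional bias. If Objective 1 governs, or to the extent that retreated gap relapsers are removed, the planned curve is too low by about the relapse risk between FW24 and entry. The figures in step 5 are for exclusion of all gap relapsers: 0.02-0.05 points at 0.2%/year, 0.11-0.26 at 1%/year, and 0.4-1.2 for front-loaded totals of 1-2%. In the front-loaded cases this is about 36% to 60% of the delayed-entry estimate; at a low constant rate it is negligible in absolute terms.

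The relapse rates, the uniform entry distribution and the follow-up lengths are assumptions. The direction was the same in every scenario that excluded gap relapsers. The 1-year window deserves weight: Amendment 03 limited new enrolment to subjects who had failed therapy (Section 2.4.1.1; Section 1.5.1 also keeps PN052 subjects), so most SVR subjects would have entered under the wider window.

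**What to change.** Reconcile Sections 2.1.1.1 and 2.5 with Sections 2.7.1.1, 3.5.4.1.1 and 3.5.5.1.1: state whether SVR24 subjects quantifiable at PN017 entry are in the primary time-to-relapse analysis.

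- **If excluded:** keep last dose as the time origin, but let each subject enter the risk set at the Visit 1 date (left-truncated Kaplan-Meier). Show numbers at risk at each Table 7 month. Report relapses found at Visit 1 as a separate count and proportion of the SVR24 subjects who enrolled.
- **If included:** keep the planned curve and label it as conditional on SVR24. State that gap relapses are dated at entry and that retreated gap relapsers are not captured. Give the left-truncated curve as a sensitivity analysis.

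The left-truncated curve assumes that entry timing is unrelated to relapse risk; say so beside it.

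The cost is a sentence or two in Section 3.5.5.1.1, aligned population wording, and an entry-time option in the program. The downside of delayed entry is smaller early risk sets, hence less precision there, and a slightly less favourable durability figure.

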GZR=grazoprevir; HCV=hepatitis C virus; LLoQ=lower limit of quantification; PN=protocol number; RAS=resistance associated substitution(s); RNA=ribonucleic acid; SVR=sustained virologic response			
^a Subjects who discontinue without relapsing will be censored at the time of discontinuation.			

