 - If any subject's HCV-RNA result is increased from prior HCV RNA result (e.g. previously TND and now TD[u] or \geq LLoQ), the subject will be asked to return to the clinic within 14 days for a Viral Confirmation Visit (Visit 8). Various scenarios, actions, and interpretations are described in [Table 5](#) below.
 - Plasma samples for HCV-RNA must be obtained and processed as instructed by the central laboratory.
- HCV Viral Resistance and Biomarker: Collected at all visits, tested as appropriate.
 - HCV population sequence analysis will be conducted, as appropriate to evaluate the presence of HCV resistance associated substitutions in NS3/4A, NS5A, or NS5B as appropriate and based on the regimen they received in the prior treatment study. Sequence analysis will be performed on any sample with HCV RNA >1000 IU/mL using the viral resistance samples that are collected and stored at every visit.

- Protein, RNA levels, metabolites, bile acids, and other markers of disease may be measured from blood samples to compare biomarkers measured during the prior treatment study to biomarkers measured at various time points during this protocol. An example of a method that may be used to measure protein levels is mass spectrometry. Plasma samples will be digested into peptides by proteases. These peptides will then be measured by mass spectrometry to determine the sequence and/or abundance of tens of thousands of peptides. The pattern of peptides will be compared between subjects who respond to drug treatment and subjects who do not respond to treatment. In addition to mass spectrometry, standard immunoassays for protein characterization such as enzyme-linked immunosorbent assays may be used to characterize levels of specific proteins identified by the mass spectrometry analysis. RNA levels will be measured in blood samples by array hybridization and/or by Polymerase Chain Reaction. Metabolites will be measured by mass spectrometry or other standard assays to identify and/or quantify thousands of metabolites in plasma. For all of the plasma biomarkers measured, associations between relapse or response to drug treatment and biomarker levels will be assessed.
- FBR Sample: Screening/Baseline visit for adult subjects who provided consent.
- HCV GT: Collected at Baseline (if HCV RNA >LLoQ) and Viral Confirmation Visit.

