 - If a subject achieved SVR at the end of follow-up in the prior treatment study and, is tested and found to have HCV RNA quantifiable during this study, that first sample with quantifiable HCV RNA will be tested for HCV GT. This is performed to determine if this is a relapse of the primary infection or a re-infection.
 - Plasma samples for HCV GT must be obtained and processed as instructed by the central laboratory.

Table 5

Actions and Interpretations Based on HCV RNA Results of Scheduled and Viral Confirmation Visits

Scheduled Visit Result	Action	Result of Viral Confirmation	Interpretation
TND	None	N/A	SVR
TD(u)	None	N/A	SVR
TD(q) Not previously determined to be a relapse, e.g. first time HCV RNA quantifiable	Viral Confirmation Visit	TND/TD(u)	SVR
		HCV RNA quantifiable	Relapse

HCV=hepatitis C virus; N/A=not applicable; RNA=ribonucleic acid; SVR=sustained virologic response; TND=target not detected; TD(q)=target detected, quantifiable; TD(u)=target detected but unquantifiable

Blood volumes collected at each visit are detailed in Appendix 6.2.1.

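### Time to relapse: a discontinuing non-relapser has two censoring dates, neither tied to the last HCV RNA result, so untested time and an unconfirmed final viremia count as relapse-free

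*Combined protocol and SAP*

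**What the plan says.** Section 3.5.5.1.1 first gives a general rule: "Subjects who do not relapse during the current study will be censored on the last visit date". Under Missing Values it adds: "Subjects who discontinue the study without relapsing will be censored at the time of discontinuation". Footnote a to Table 3 (Section 2.7.1.1) repeats the second rule: "Subjects who discontinue without relapsing will be censored at the time of discontinuation". The Missing Values paragraph opens with "Only observed data will be included in the analyses" and then states that "subjects missing an HCV RNA evaluation at any particular visit will be considered a non-relapser for that visit".

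The event is a confirmed HCV RNA at or above the LLoQ that is not a re-infection (Sections 2.5 and 3.5.3.1.1). On confirmation, Section 2.5 says "Confirmation is defined as an HCV RNA that is target detected, quantifiable (TD[q]) from a separate blood draw repeated in approximately 4 weeks", while Section 3.3.1.1 says "the subject will be asked to return to the clinic within 14 days for a Viral Confirmation Visit". Tables 2 and 5 classify a first quantifiable result (in Table 5, "Not previously determined to be a relapse, e.g. first time HCV RNA quantifiable") only by the confirmation result: SVR if it is TND or TD(u), relapse if it is quantifiable. Neither table has a row for a confirmation visit that does not take place.

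Sections 2.7.1.1 and 3.5.3.1.1 also plan a percentage of subjects remaining below the LLoQ, without mentioning confirmation.

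Two provisions limit the problem. Sections 3.2.4.8 and 3.2.4.8.1, and footnote 11 of the adult flow chart (Section 1.7.1), call for final-visit procedures at discontinuation. Section 3.3.1.1 schedules HCV RNA at every visit.

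**The concern.** A subject is known to be relapse-free only up to the last HCV RNA below the LLoQ. A subject who discontinues without relapsing meets both censoring rules, no priority between them is stated, and neither refers to that result. Scoring a missing result as non-relapse also sits badly with restricting the analysis to observed data. A departure from schedule at exit therefore adds time at risk in which relapse could not have been detected.

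The unconfirmed case has a similar consequence. If a first TD(q) is never followed by a confirmation draw, the subject's last known result is viremic, yet the subject is censored as relapse-free at or after it. This is plausible here. After Amendment 03, subjects who entered below the LLoQ (except those from PN052) were stopped at their next scheduled visit, so a first TD(q) at that visit needs a return after discontinuation to be confirmed.

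Time to relapse is the primary adult efficacy estimate, and Section 3.5 says that no separate SAP will follow. As written, two programmers could derive different censoring dates from the same data.

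**Working it through.** The plan states no relapse, missing-result or non-confirmation rate and no sample size, so there is no figure to reproduce. From the documents: visits are six-monthly with HCV RNA at each, giving six visits after entry over three years and ten over five years (PN052). All rates below are assumptions.

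**Which date applies**

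| At exit | Last visit date | Time of discontinuation | Last HCV RNA <LLoQ |
|---|---|---|---|
| Visit held, RNA <LLoQ | exit visit | exit visit | exit visit |
| Visit held, no RNA result | exit visit | exit visit | previous tested visit |
| Visit not held | previous visit | possibly later | previous tested visit |

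In the second row both stated dates credit untested time. In the third row only the discontinuation date does, provided that the previous visit was tested.

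**Exit visit held, HCV RNA missing.** A relapse arising before the exit visit is lost when that result is missing, but the subject still counts as at risk. For low hazards:

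relative shortfall = share missing × mean over visits of (fraction of those at risk who exit at that visit).

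- Six visits, all followed to the end: 1/6 = 0.167.
- Six visits, exits spread evenly: (1/6 + 1/5 + 1/4 + 1/3 + 1/2 + 1)/6 = 2.45/6 = 0.408.
- Ten visits: 1/10 = 0.100, or 2.929/10 = 0.293 with spread exits.

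| Follow-up | Exits | 5% missing | 20% missing |
|---|---|---|---|
| 3 years | all at end | 0.8% low | 3.3% low |
| 3 years | spread | 2.0% low | 8.2% low |
| 5 years | all at end | 0.5% low | 2.0% low |
| 5 years | spread | 1.5% low | 5.9% low |

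At 1 relapse per 100 person-years the true three-year risk is 1 − exp(−0.03) = 2.955%, so the largest shortfall is 0.082 × 2.955 = 0.24 points. Over five years, 1 − exp(−0.05) = 4.877%, and 0.059 × 4.877 = 0.29 points. At 0.2 per 100 person-years it is 0.082 × 0.598 = 0.05 points over three years.

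Simulation (1.5–2 million subjects per setting, Monte Carlo standard error about 0.02 points) agrees. With 20% missing and spread exits, the plan reads 2.695% and last-RNA censoring 2.927% (truth 2.955%). Over five years the figures are 4.596% and 4.876% (truth 4.877%).

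**Exit visit not held.** The two stated dates now give different answers. With discontinuation dated when the visit was due and 20% of exit visits not held, spread exits give 2.961% (last visit) against 2.722% (discontinuation). With 5% not held and all followed, the figures are 2.943% and 2.918%. The gap is therefore 0.02–0.24 points.

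**Final TD(q) never confirmed.** The same factor applies. If 10–30% of viremias first seen on the last sample are unconfirmed, the shortfall is 1.7–5.0% (0.167) or 4.1–12.2% (0.408), which is 0.05–0.36 points at 1 per 100 person-years. Moving the censoring date alone does not recover this (2.605% against 2.607%).

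**Percentage remaining <LLoQ, read literally.** If 0.1–0.5% of samples are transient TD(q), six samples give 6 × 0.1 = 0.6 to 6 × 0.5 = 3.0 points below the confirmed-relapse classification at Month 36. Simulation with 10% unconfirmed gives 96.44% against 97.06%, and 94.18% against 97.10%.

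**The case against.** The strongest reply is that the two sentences are a general rule and a specific one, and that they matter only when procedures are not followed. The exit visit is required, HCV RNA is due at it, and most SVR subjects were stopped under Amendment 03 at a scheduled visit, where the dates should normally coincide. This stands for compliant subjects. But a missing-data rule exists for the others, and the general-and-specific reading still leaves a discontinuation date that can fall after the last test.

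Three stronger readings are tempting, and the documents do not support them:

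- **An unconfirmed TD(q) has no class at all.** Sections 2.5, 3.5.3.1.1 and 3.5.5.1.1 together make it a non-relapse by default. What is missing is an explicit statement and a censoring date before the viremic sample.
- **The event-date wording is a second, unconfirmed definition of relapse.** Section 2.7.1.1 cross-refers to Section 2.5 for this date, and in Section 3.5.3.1.1 the date follows a definition that requires confirmation.
- **Two primary summaries conflict.** Section 2.7.1.1 presents the percentage below the LLoQ as additional to time to relapse, and Table 3 lists only time to relapse for durability. The 0.6–3.0 point gap therefore belongs to a supplementary figure.

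It is also fair that last-RNA censoring is not always closer to the truth. With results missing at every visit, spread exits and a truth of 2.955%, 5, 10 and 20% missing give 2.940, 3.018 and 3.110% under last-RNA censoring, against 2.879, 2.885 and 2.809% under the plan. At 20% it is slightly further off, in the other direction.

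**Conclusion.** The point holds as a defect of derivation. Section 3.5.5.1.1 states two censoring dates for one subject, ties neither to the last HCV RNA result, and scores missing results as non-relapse. When the exit visit lacks a result, or is not held and the discontinuation date is used, the relapse estimate can only be lowered. By default, an unconfirmed final TD(q) is censored as relapse-free at or after a viremic result.

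The effect on the primary estimate is small: about 0.3 points at most from missing exit results and 0.36 points from unconfirmed viremia. These figures assume 1 relapse per 100 person-years, 5–20% missing and 10–30% unconfirmed. With few events, a single classification can still show. In an assumed cohort of 200 with one confirmed and one unconfirmed case at Month 24, the Month 36 estimate is 0.87% or 1.74% depending on how the second case is counted.

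A reader might infer that the durability conclusion is at risk. The documents do not support that: the analysis is descriptive, without hypothesis tests or a planned sample size.

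**What to change.** - In Section 3.5.5.1.1 and footnote a of Table 3, state one censoring date for non-relapsers: the last HCV RNA below the LLoQ, before any new HCV therapy. Delete the sentence that scores a missing result as non-relapse.
- Keep confirmed, non-reinfection relapse as the event. State that an unconfirmed final TD(q) is censored at the preceding result below the LLoQ.
- Report the number of unconfirmed final TD(q) results and of exit visits without HCV RNA. Add a sensitivity analysis that counts unconfirmed final TD(q) as relapse unless shown to be re-infection.
- Apply the classification in Tables 2 and 5 to the percentage remaining below the LLoQ, and state how that percentage treats an unconfirmed final TD(q).
- Reconcile the confirmation intervals in Sections 2.5 and 3.3.1.1, so that an unconfirmed result can be coded the same way throughout.

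The cost is a few sentences, one derivation, two counts and one table. Follow-up becomes slightly shorter, and the estimate can modestly overshoot if results are often missing at every visit. The sensitivity analysis must be labelled an upper bound because it also counts transient TD(q). At 0.2 relapses per 100 person-years, with 30% unconfirmed and 0.5% of samples transient, it reads 0.95% against 0.52% under the plan and a truth of 0.60%.
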